6.6.2. Deaths

All deaths, deaths within 30 days after last dose of study drug, deaths within 30 days after first dose of study drug as well as the primary reason for death, will be tabulated based on information from the “Death Details” and “Disposition Long-term Follow-Up” eCRFs.

- Number of deaths.
- Number of deaths within 30 days after *last* dose of study treatment.
- Number of deaths within 30 days after *first* dose of study treatment.
- Primary cause of death.

In addition, if there are ≥ 5 deaths due to COVID-19, a separate death summary will be created.

Date and cause of death will be provided in patient data listing together with selected dosing information (study treatment received, date of first/last administration, dose).

6.6.3. Laboratory Data

Laboratory results will be converted to International System of Units (SI) units which will be used for applying toxicity grades and for all summaries.

As described in [Section 3.3](#), baseline is defined as the last completed assessment prior to date of first dose for the safety assessments. If there are multiple assessments that meet the baseline definition on the same day without the ability to determine which was truly last, then the worst grade will be assigned as the baseline grade.

Laboratory results will be programmatically classified according to NCI-CTCAE version 4.03. Non-numerical qualifiers will not be taken into consideration in the derivation of grade (eg, hypokalemia Grade 1 and Grade 2 are only distinguished by a non-numerical qualifier and therefore Grade 2 will not be derived). In summary statistics the number and percentage of patients corresponding to grades that only include non-quantitative criteria will be displayed as a blank or NA (not assessed) rather than 0. If there is any overlap between

grade criteria (eg, CTCAE grading criteria for Creatinine Increased – a value can fall into one range based on comparison to ULN and another range based on comparison to baseline), the highest (worst) grade would be assigned to that record. Grade 5 is defined in the CTCAE criteria guidance as an event with an outcome of death. Since laboratory data does not collect an outcome, Grade 5 is not used when programmatically grading laboratory data.

Grade 0 or Outside Toxicity Reference (OTR) is not defined specifically in the CTCAE guidance. However, programmatically this is used as a category to represent those patients who did not meet any of the Grades 1 to 4 criteria. If the laboratory value is evaluable for CTCAE criteria grading (numeric value is present, valid units and ranges are present as required to allow conversion to standard units and grading), and does not qualify for any of the Grade 1-4 criteria for a given lab test, then the value is assigned as Grade 0 or OTR.

Abnormalities will be described using the worst grade post-baseline. When determining the maximum post-baseline grade for a given patient and CTCAE test, the maximum across all analytes and assessments contributing to that CTCAE test will be used. Several laboratory tests have bi-directional grading criteria defined so that both low (hypo) and high (hyper) values can be graded separately. Each criterion will be summarized separately. In the cases where a value is graded as a Grade 1, 2, 3, or 4 for one of the directions, that value will also be assigned as a Grade 0 for the opposite direction for that test. For example, a value meeting the criteria for Grade 3 Hypercalcemia will be classified as a Grade 0 Hypocalcemia. For CTCAE terms that can be derived using one of several laboratory tests, the maximum post-baseline grade for a given patient and CTCAE term will be the maximum across all possible laboratory tests.

For **WBC differential counts** (total neutrophil [including bands], lymphocyte, monocyte, eosinophil, and basophil counts), the absolute value will be used when reported by the lab. When only percentages are available (this is mainly applicable for neutrophils and lymphocytes, because the CTCAE grading is based on the absolute counts), the absolute value is derived as follows:

$$\text{Derived differential absolute count} = (\text{WBC count}) \times (\text{Differential \%value}/100)$$

If the investigator reports both the absolute and % value for Neutrophils or Lymphocytes from the same laboratory sample date and patient, ONLY the absolute value will be graded. The % value will not be graded in this scenario.

If the % value is converted to the differential absolute count for grading and the LLN for the differential absolute count is not available (only LLN for % is available) then Grade 1 will be assigned if the following conditions are met:

- Lymphocyte count decreased:
 - derived absolute count does not meet Grade 2-4 criteria, and
 - % value < % LLN value, and

- derived absolute count $\geq 800/\text{mm}^3$.
- Neutrophil count decreased:
 - derived absolute count does not meet Grade 2-4 criteria, and
 - % value < % LLN value, and
 - derived absolute count $\geq 1500/\text{mm}^3$.

For **calcium**, CTCAE grading is based on Corrected Calcium and Ionized Calcium. Corrected Calcium is calculated from Albumin and Calcium as follows:

- Corrected Calcium (mg/dL) = measured total calcium (mg/dL) – $0.8 \times [\text{serum albumin (g/dL)} - 4]$.

Laboratory toxicities will be tabulated using descriptive statistics (number of patients and percentages). If both central and local labs are collected for a subject, summaries of worst on-treatment abnormalities will be based on both local and central lab data.

Additional laboratory results that are not part of NCI-CTCAE will be presented according to the categories: below normal limit, within normal limits and above normal limit (according to the laboratory normal ranges). The following summary tables will be created:

- Shift summary of laboratory parameters during the on-treatment period by maximum CTCAE grade.
- Shift summary of laboratory parameters from \leq Grade 2 at baseline to \geq Grade 3 post-baseline.
- Shift summary of laboratory test results with no CTCAE criteria by worst on-treatment assessment.

All laboratory test results will be presented in a data listing sorted by patient identifier, laboratory test, and date/time of collection. The CTCAE grades and the classifications relative to the laboratory reference ranges will be presented. Values outside laboratory normal ranges will be flagged where appropriate and the central laboratory data and local laboratory data will be flagged accordingly.

Drug Induced Liver Toxicity

Alanine aminotransferase (ALT), aspartate aminotransferase (AST), Alkaline Phosphatase (ALP), and total bilirubin (TBILI) are used to assess possible drug induced liver toxicity. The ratios of test result over the ULN will be calculated and classified for these three parameters during the on-treatment period.

Summary of liver function tests will include the following categories. The number and percentage of patients with each of the following during the on-treatment period will be summarized:

- $ALT \geq 3 \times ULN$, $ALT \geq 5 \times ULN$, $ALT \geq 10 \times ULN$, $ALT \geq 20 \times ULN$.
- $AST \geq 3 \times ULN$, $AST \geq 5 \times ULN$, $AST \geq 10 \times ULN$, $AST \geq 20 \times ULN$.
- $(ALT \text{ or } AST) \geq 3 \times ULN$, $(ALT \text{ or } AST) \geq 5 \times ULN$, $(ALT \text{ or } AST) \geq 10 \times ULN$, $(ALT \text{ or } AST) \geq 20 \times ULN$.
- $TBILI \geq 2 \times ULN$.
- Concurrent $ALT \geq 3 \times ULN$ and $TBILI \geq 2 \times ULN$.
- Concurrent $AST \geq 3 \times ULN$ and $TBILI \geq 2 \times ULN$.
- Concurrent $(ALT \text{ or } AST) \geq 3 \times ULN$ and $TBILI \geq 2 \times ULN$.
- Concurrent $(ALT \text{ or } AST) \geq 3 \times ULN$ and $TBILI \geq 2 \times ULN$ and $ALP > 2 \times ULN$.
- Concurrent $(ALT \text{ or } AST) \geq 3 \times ULN$ and $TBILI \geq 2 \times ULN$ and $ALP \leq 2 \times ULN$ or missing.

Concurrent measurements are those occurring on the same date.

Categories will be cumulative, ie, a patient with an elevation of $AST \geq 10 \times ULN$ will also appear in the categories $\geq 5 \times ULN$ and $\geq 3 \times ULN$. Liver function elevation and possible Hy's Law cases will be summarized using frequency counts and percentages.

An evaluation of Drug-Induced Serious Hepatotoxicity (eDISH) plot will also be created, with different symbols for different treatment arms, by graphically displaying:

- Peak serum $ALT (/ULN)$ vs peak total bilirubin ($/ULN$) including reference lines at $ALT = 3 \times ULN$ and total bilirubin $= 2 \times ULN$.
- Peak serum $AST (/ULN)$ vs peak total bilirubin ($/ULN$) including reference lines at $AST = 3 \times ULN$ and total bilirubin $= 2 \times ULN$.

In addition, a listing of all TBILI, ALT, AST and ALP values for patients with a post-baseline $TBILI \geq 2 \times ULN$, $ALT \geq 3 \times ULN$ or $AST \geq 3 \times ULN$ will be provided.

6.6.4. Vital Signs

Vital signs data includes weight, pulse, systolic blood pressure (BP), and diastolic BP. Measurements were only to be provided once per timepoint. If multiple assessments are provided per timepoint, the maximum value will be used for reporting.

The following criteria define clinically notable vital sign abnormalities:

- Clinically notable elevated values:
 - Systolic BP: ≥ 160 mmHg and an increase ≥ 20 mmHg from baseline;
 - Diastolic BP: ≥ 100 mmHg and an increase ≥ 15 mmHg from baseline;
 - Heart rate (collected as pulse rate in the vital signs eCRF): ≥ 120 bpm with increase from baseline of ≥ 15 bpm;
 - Weight: increase from baseline of $\geq 10\%$;
 - Body temperature [C]: ≥ 37.5 C.
- Clinically notable low values
 - Systolic BP: ≤ 90 mmHg with decrease from baseline of ≥ 20 mmHg;
 - Diastolic BP: ≤ 50 mmHg with decrease from baseline of ≥ 15 mmHg;
 - Heart rate (collected as pulse rate in the vital signs eCRF): ≤ 50 bpm with decrease from baseline of ≥ 15 bpm;
 - Weight: $\geq 20\%$ decrease from baseline;
 - Body temperature [C]: ≤ 36 C.

All assessments, including unscheduled assessments will be considered. A patient can be included in multiple categories if different criteria are met at different timepoints.

Number and percentage of patients with at least one post-baseline vital sign abnormality will be summarized.

Patients with clinically notable vital sign abnormalities will be presented in a data listing. Clinically notable values will also be flagged in this listing.

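### SAP 6.6.4 reduces duplicate vital-sign readings to the maximum, which is the least severe choice for the low-value criteria

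*SAP*

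**What the plan says.** SAP 6.6.4 opens with the expectation that duplicates should not arise: "Measurements were only to be provided once per timepoint". It then says what happens if they do: "If multiple assessments are provided per timepoint, the maximum value will be used for reporting". The rule carries no exception by direction or by parameter.

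The section goes on to define abnormalities on both sides. Under "Clinically notable low values" it lists five criteria:

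- systolic pressure ≤90 mmHg with a fall of ≥20
- diastolic pressure ≤50 mmHg with a fall of ≥15
- pulse ≤50 bpm with a fall of ≥15
- weight down by ≥20%
- temperature ≤36 C

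Three further sentences govern how the criteria are used: "All assessments, including unscheduled assessments will be considered"; "A patient can be included in multiple categories if different criteria are met at different timepoints"; and "Number and percentage of patients with at least one post-baseline vital sign abnormality will be summarized". The section's listing covers only patients already classed as notable.

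**The concern.** A single direction-blind reduction is being asked to serve two opposite sets of criteria. For a high criterion the maximum is the conservative choice. For a low criterion it is the most reassuring choice available.

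That departs from the SAP's practice elsewhere. SAP 5.2.7 speaks of worst-case on-treatment values for safety analyses. SAP 6.6.3 grades the low and high directions of a laboratory test separately, and assigns the worst grade when same-day baseline values cannot be ordered.

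What is at stake is one descriptive table and its listing. Changes in vital signs are among the primary Safety Lead-in endpoints and the secondary safety endpoints (protocol section 3). The count of patients with a notable abnormality is the only vital-sign summary that SAP 6.6.4 specifies. For the low criteria, any error from this rule can only reduce that count.

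**Working it through.** The plan gives no figure to reproduce here, so the check applies the SAP 6.6.4 criteria to pairs of readings at one timepoint.

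**Main example** (values chosen for illustration). Baseline systolic 120 mmHg; readings 85 and 95 mmHg.
- Maximum: 95 > 90, so not notable.
- Minimum: 85 ≤ 90 and 120 − 85 = 35 ≥ 20, so notable.

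**All five low criteria** (values again illustrative):

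| Parameter | Baseline | Readings | Maximum rule | Minimum rule |
|---|---|---|---|---|
| Systolic, mmHg | 120 | 84, 96 | not flagged | flagged |
| Diastolic, mmHg | 75 | 48, 56 | not flagged | flagged |
| Pulse, bpm | 72 | 48, 58 | not flagged | flagged |
| Weight, kg | 80 | 63.5, 64.5 | not flagged (19.4% loss) | flagged (20.6% loss) |
| Temperature, C | 36.8 | 35.8, 36.3 | not flagged | flagged |

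Five mirror-image high pairs (for example systolic 152 and 164 mmHg from a baseline of 120) are all flagged by the maximum, so the elevated side already works.

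**Conditional size.** Suppose a timepoint has two independent readings, each with chance q of meeting a low criterion. The maximum rule flags the timepoint only if both do, with probability q². At least one low reading occurs with probability 1 − (1 − q)².
- q = 0.10: 1.0% flagged, against 19.0% with any low reading
- q = 0.25: 6.3% against 43.8%
- q = 0.50: 25.0% against 75.0%

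The share of low timepoints missed is 1 − q²/[1 − (1 − q)²] = 2(1 − q)/(2 − q). For systolic pressure with baseline 120, any reading ≤90 is a fall of at least 30, so only the 90 mmHg threshold matters. Assume normally distributed readings.
- True value 85, within-timepoint SD 4: q = Φ(1.25) = 0.894; missed share 19%.
- True value 90, any SD: q = 0.5; missed share 67%.
- True value 95, SD 4: q = Φ(−1.25) = 0.106; missed share 94%.

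All of these are conditional on a duplicate existing. The values of q, the means, the SDs and independence are assumptions; the documents give none of them.

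**Baseline.** SAP 6.6.4 does not say whether its rule also applies to repeated baseline readings, and SAP 3.3 takes the last completed assessment before first dose. The choice matters. With baseline readings of 125 and 145 and 162 mmHg on treatment, the rise is 17 from the maximum (not notable) and 37 from the minimum (notable). With baseline readings of 105 and 115 and 90 mmHg on treatment, the fall is 25 from the maximum (notable) and 15 from the minimum (not notable).

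**The case against.** **Duplicates are not expected.** The rule is a tie-break for something the SAP says should not happen, and protocol 7.3.5 contains no repeat-measurement procedure. This stands, and it limits the likely effect.

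**The sentence on considering all assessments may already protect low values.** If it governs the criteria, and the maximum governs only the value displayed, nothing is lost. A recheck entered as unscheduled might also count as a separate assessment and not be collapsed. These readings are possible, but the SAP does not say that one sentence overrides the other. Because it frames the criteria by timepoint, the more natural reading is that every timepoint is considered after reduction to one value. Two programmers could reasonably produce different counts.

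**Important events have another route.** Under protocol 7.3.5 an abnormal vital sign after first dose is an adverse event if it is clinically meaningful, symptomatic, or leads to therapy or a treatment change. Protocol 8.4.3 also promises listings of all safety data. Both points stand. They narrow what is lost to isolated readings in the SAP 6.6.4 output, but they do not correct that output.

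**Two stronger readings are tempting but not supported.** A reader might infer that every low reading with a higher repeat is lost. That is not so: with baseline 120 and readings of 82 and 88 mmHg the maximum still meets the criterion, and a patient flagged at another timepoint is still counted. A reader might also infer that repeats are taken mainly after abnormal first readings, so that the table is systematically reassuring. That is plausible, but nothing in the documents says so.

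**Conclusion.** The defect holds as a matter of wording. Followed as written, SAP 6.6.4 applies the least severe reading to all five low criteria whenever a timepoint has more than one reading. A patient is lost from the table only when three things coincide: a duplicate exists, the higher reading fails the low criterion, and no other timepoint flags the patient. For weight this needs same-timepoint readings on either side of a 20% loss, which adds little in practice.

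The direction of the error is certain. Its size is not: without a duplicate frequency the effect on the table cannot be estimated and may be small. The conditional percentages show only that, where duplicates do occur near a threshold, the choice of rule matters. The primary response analysis and the sample size do not depend on any of this. It is worth correcting because the SAP states a rule and the rule works for only half of the criteria it serves.

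**What to change.** Replace the duplicate-reading sentence in SAP 6.6.4 with: *Where more than one post-baseline reading exists at a timepoint, the highest is used for the elevated criteria and the lowest for the low criteria; baseline follows Section 3.3.*

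This also reconciles the rule with the sentence on considering all assessments. With baseline fixed, each low criterion becomes easier to meet as the value falls, so the lowest reading meets it exactly when at least one reading does; the same holds in reverse for the highest reading and the elevated criteria. The result is therefore the same as applying the criteria to every reading.

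The cost is one SAP sentence and a direction flag in the derivation program. No new data, protocol amendment or change to the other analyses is needed.

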6.6.5. Electrocardiograms

Potential effects of treatment with study drug on ECG parameters will be assessed by ECG interval analysis of heart rate, pulse rate, QRS, QT, and QT interval corrected for heart rate (QTc). Triplicate measurements will be obtained at screening and pre-dose on Cycle 1 Day 1 according to the schedule of assessments in the protocol.

The average of the machine-read triplicate ECG measurements collected closest to but prior to the first dose of study drug will serve as each patient's baseline QT, QTcF, and heart rate value for all post-dose comparisons. The QT, QTcF, and heart rate data collected on the eCRF page will be used in the summary.

Number and percentages of patients with clinically notable ECG values during the on-treatment period will be summarized. The clinically notable ECG values are defined in Table 6.

Patients with clinically notable ECG values will be presented in a data listing. Clinically notable values will also be flagged in this listing.

Table 6: Clinical Notable ECG Criteria

Parameter	Criterion
QT, QTcF	increase from baseline >30 ms increase from baseline >60 ms new >450 ms new >480 ms new >500 ms
Heart rate	Increase from baseline >25% and to a value >100 bpm Decrease from baseline >25% and to a value <50 bpm

6.6.6. Neurological Symptoms

Neurological symptom data will be presented in a data listing.

6.6.7. ECOG Performance Status

ECOG performance status at each time point will be presented in a data listing.

6.6.8. Echocardiogram/Multi-gated Acquisition

Left ventricular ejection fraction (LVEF) abnormalities are defined according to CTCAE grade version 4.03. Patients will be considered as having a LVEF abnormality if the worst post value is grade 2, 3 or 4 according to the following classification:

- Grade 0: Non-missing value below Grade 2.
- Grade 2: LVEF between 40% and 50% or absolute change from baseline between -10% and < -20%.
- Grade 3: LVEF between 20% and 39% or absolute change from baseline lower than or equal to -20%.
- Grade 4: LVEF lower than 20%.

A shift table using CTCAE grades to compare baseline to the worst post-baseline LVEF value will be produced.

Different modalities to assess LVEF might be used for the same patient. The shift table will be provided regardless of the modality.

All LVEF assessments will be presented in a data listing.

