6.6. High-dose Safety Assessment

After 9 evaluable patients in the Safety Lead-in have completed one 28-day cycle of treatment, safety assessments will be conducted. All toxicities will be assessed for severity by the Investigator using CTCAE v4.03. Evaluable patients for the Safety Lead-in cohort must have either:

- experienced a DLT (Table 7) or
- received at least 75% of the planned cumulative dose of both study drugs during Cycle 1.

The Sponsor and participating Investigators will perform ongoing reviews of patient safety data through regular teleconferences approximately weekly during the Safety Lead-in. Once 9 evaluable patients are available for assessment, the Sponsor will convene a joint teleconference with participating Investigators. If the high-dose treatment is found safe based on 9 evaluable patients, subsequent patients will be randomized 1:1 to receive either the standard or high-dose treatment. If the high-dose treatment is determined not to be safe, enrollment will proceed with the standard-dose treatment as outlined in Section 4.1. The high-dose treatment will be considered safe if the rate of DLTs (Table 7) observed in the first cycle of treatment in the Safety Lead-in is $< 33\%$.

Table 7. Criteria for Defining Dose-limiting Toxicities

DLT Definition
A DLT is defined as any AE or laboratory abnormality that is not explained by underlying disease, disease progression, intercurrent illness, or concomitant therapies that either meets the criteria described below or results in the inability to tolerate at least 75% of the planned dose of binimetinib or encorafenib during Cycle 1.
Specific DLT Criteria
Cardiac disorders 
 • Absolute decrease of LVEF > 10% compared to baseline and the LVEF is below the institution's LLN • LV systolic dysfunction Grade ≥ 3 • Other cardiac disorders Grade ≥ 3
Vascular disorders 
 • Grade 3 hypertension for > 14 consecutive days • Grade 4 hypertension
Skin and subcutaneous tissue disorders^a 
 • Rash, hand foot skin reaction (HFSR) or photosensitivity CTCAE Grade 3 for > 14 consecutive days despite maximal skin toxicity treatment (as per local practice) • Rash, HFSR or photosensitivity CTCAE Grade 4

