7.3.11. Echocardiogram/Multi-gated Acquisition

Cardiac ejection fraction will be assessed by transthoracic ECHO or MUGA at the time points specified in SoA ([Table 3](#)).

The same method should be used throughout the study. Patients who develop signs/symptoms of congestive heart failure at any point during the study are required to have an evaluation of LVEF measurements by ECHO or MUGA.

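### The Grade 2 LVEF change limit in SAP 6.6.8 has its inequality reversed, so coded literally the shift table grades some falls of 10 to under 20 points as Grade 0; it also pools modalities without a flag

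*SAP*

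**What the plan says.** SAP 6.6.8 (Echocardiogram/Multi-gated Acquisition) grades LVEF in four categories, citing CTCAE version 4.03 as the source:

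- "Grade 0: Non-missing value below Grade 2"
- "Grade 2: LVEF between 40% and 50% or absolute change from baseline between -10% and < -20" (per cent)
- "Grade 3: LVEF between 20% and 39% or absolute change from baseline lower than or equal to -20" (per cent)
- "Grade 4: LVEF lower than 20" (per cent)

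The grades feed one output: "A shift table using CTCAE grades to compare baseline to the worst post-baseline LVEF value will be produced". All LVEF values are also listed.

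On modality the SAP adds: "Different modalities to assess LVEF might be used for the same patient. The shift table will be provided regardless of the modality". Protocol 7.3.11 says: "The same method should be used throughout the study".

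**The concern.** The Grade 2 and Grade 3 change limits do not fit together. A change below -20% already belongs to Grade 3, so the Grade 2 limit as written covers no fall of its own. Grade 0 is the residual category, so any fall that the Grade 2 limit should catch, and that no absolute LVEF band catches, is reported as no abnormality.

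Modality is a second and smaller matter. Part of the grade is a difference from baseline. If baseline is by one method and a later value by another, any between-method difference enters that grade. The SAP foresees mixed methods but plans no flag, footnote or same-modality version of the table.

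The stake is how far the measured LVEF summary can be relied on. Left ventricular dysfunction is a named risk of the combination: Protocol 2.2.3 reports ejection fraction decreases in 7% of patients and Grade 3 dysfunction in 1.6%. The shift table is the only planned tabulation of measured LVEF.

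**Working it through.** The plan states no LVEF figure to reproduce, so the check applies the grading rule itself.

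**Inputs.** The four grade definitions come from SAP 6.6.8. The lowest eligible baseline is 50%, because Protocol 5.2 excludes LVEF below 50%. Let b be baseline, v the post-baseline value and d = v - b.

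**Literal Grade 2 change limit.** It requires d <= -10 and d < -20, which reduces to d < -20. Grade 3 takes d <= -20. Every d that meets the first also meets the second, so the Grade 2 change limit is redundant.

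**Which falls are lost.** Take a fall f = b - v with 10 <= f < 20.

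- If v is 40% to 50%, the absolute Grade 2 band still applies.
- If v is 20% to 39%, the absolute Grade 3 band still applies.
- If v is above 50%, no criterion is met and the value is Grade 0.

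The last case needs b - f > 50 with f at least 10, so b > 60. When b >= 70, b - f > 50 for every f under 20, so all such falls are lost.

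Examples: 65% to 53% (d = -12) and 70% to 55% (d = -15) are Grade 0 as written and Grade 2 with the sign corrected.

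**Grid check.** Integer baselines 50 to 75 (26 values) with integer falls 10 to 19 (10 values) give 26 x 10 = 260 combinations:

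| Reading of the Grade 2 change limit | Grade 0 | Grade 2 | Grade 3 |
|---|---|---|---|
| Literal (d < -20) | 105 | 110 | 45 |
| Corrected (-20 < d <= -10) | 0 | 215 | 45 |
| Lenient (any d <= -10, Grade 3 taking precedence) | 0 | 215 | 45 |

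The 105 can be counted by hand. Baselines 61 to 69 lose 1, 2, ..., 9 falls, which sum to 45. Baselines 70 to 75 lose 10 each, which is 60. 45 + 60 = 105. These are counts of combinations, not patient proportions.

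**Gap between 39% and 40%.** If values are recorded with decimals, v = 39.5% lies in neither the 20% to 39% band nor the 40% to 50% band. From b = 52%, d = 39.5 - 52 = -12.5. The literal rule gives Grade 0. Correcting only the sign gives Grade 2. Closing the band gives Grade 3.

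**Modality.** Protocol 7.3.11 asks for one method per patient; SAP 6.6.8 allows for several and grades the difference between them as change. The documents give no between-method bias, no variability and no expected frequency of switching, so no size can be put on this part.

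**The case against.** The strongest reply is that the Grade 2 line is a slip with one sensible meaning. Read as the size of a fall, it says 10 to under 20 points, which meets the Grade 3 line exactly, and a programmer who reads it that way loses nothing. That is correct, and it means the misgrading is conditional on literal coding. It does not remove the defect: an analysis rule that yields two different tables depending on who codes it should be settled in the SAP.

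On modality, the protocol says *should* and gives no reason, the SAP says only that methods *might* differ, and pooling is openly prespecified. That also stands. Dropping the change criterion for patients who switch would carry its own error, because a true fall from 70% to 55% in such a patient would become Grade 0.

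A reader might also infer that the table is wrong because it ignores the protocol's own LVEF event, "Absolute decrease of LVEF > 10% compared to baseline and the LVEF is below the" institutional lower limit of normal. The documents do not support that. Table 7 defines DLTs and Appendix 3 governs binimetinib dosing; neither prescribes how LVEF is summarised. Grading by CTCAE is a legitimate choice, and the corrected rule would still grade 72% to 61% (d = -11) as Grade 2.

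**Conclusion.** The reversed inequality is a real error in a stated analysis rule and should be corrected before programming. Under literal coding, falls of 10 to under 20 points that end above 50% are reported as Grade 0; this is possible only from a baseline above 60%. Under the evident intended reading, none are missed. The reversal is judged from the adjacent Grade 3 line alone, because the CTCAE text is not in the documents.

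The modality point holds as a missing transparency step. A reader might infer that method switches will materially inflate the abnormality count. The documents give no figures for this, and a between-method bias in the other direction would hide falls instead.

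Nor should the point be read as undermining the trial's safety decisions. DLTs and dose modification use their own LVEF criteria, adverse events are tabulated separately (SAP 6.6.1), raw LVEF values are listed, and the primary endpoint does not depend on this table. The consequence is confined to one descriptive safety table.

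**What to change.** In SAP 6.6.8, state the grades as:

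- Grade 2: LVEF 40% to 50%, or -20% < absolute change from baseline <= -10%.
- Grade 3: LVEF 20% to <40%, or absolute change from baseline <= -20%.

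The Grade 3 wording also closes the gap between 39% and 40%.

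Keep the planned shift table across modalities as the main table. Footnote the number of patients whose modality changed after baseline, and add the same table restricted to post-baseline values obtained by the baseline modality. Patients who switch then stay in the main table, and the reader can see whether they drive any shift.

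The cost is a wording correction, one footnote and one extra descriptive table. No new assessments are needed.
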